1.2 Schema

The study design is depicted in Figure 1.

Figure 1 Study Design

1. The enrollment period may last up to approximately 30 months from the time of enrollment of the first participant. Additionally, data cutoff may occur when the last evaluable participant (see Section 1.1 for definition of evaluable) enrolled in the study has completed the Week 16 imaging assessment or discontinues prior to Week 16 imaging assessment, whichever occurs first.
2. If no objective responses are observed at the time of enrollment of the ninth evaluable participant in a specific cohort or other tumor type, enrollment will be paused in said cohort or other tumor type until the IA for these 9 evaluable participants is completed. If at least 1 objective response is observed at the time of enrollment of the ninth evaluable participant in a specific cohort or other tumor type, enrollment may continue in said cohort or other tumor type.
3. In addition to the futility rules above, the enrollment of 3 target tumor cohorts will stop if a lack of antitumor activity is concluded for the corresponding tumor cohort in Study E7080-A001-216.

1.3 Schedule of Activities

Table 1 Schedule of Activities

Study Period	Screening	Intervention Cycle = 28 Days								EOT	Post-treatment Visits			NOTES
		1			2		3	4	5 – last		Safety FU	Efficacy (Imaging) FU Visits	Survival FU	
Cycle Day		1	8	15	1	15	1	1	1	At DC	30 days after last dose	Q8W for 24 weeks, then Q12W	Q12W	
Scheduling Window	-28 to -1		±2	±2	±2	±2	±2	±2	±2		±7	±7	±7	
Administrative Procedures														
Informed Consent/ Assent	X													Documented informed consent/assent may be obtained up to 4 weeks prior to C1D1 and must be obtained prior to performing any protocol-specified procedure. Results of a test performed as part of routine clinical management are acceptable in lieu of a screening test if performed within the specified time frame for screening.
Inclusion/ Exclusion Criteria	X													See Appendix 7 for country-specific requirements.
Participant Identification Card	X													At the time of allocation, site personnel will add the allocation number to the identification card.
Demographics	X													

Study Period	Screening	Intervention Cycle = 28 Days								EOT	Post-treatment Visits			NOTES
		1			2		3	4	5 – last		Safety FU	Efficacy (Imaging) FU Visits	Survival FU	
Visit Timing/ Cycle No.		1	8	15	1	15	1	1	1	At DC	30 days after last dose	Q8W for 24 weeks, then Q12W	Q12 W	
Cycle Day		1	8	15	1	15	1	1	1					
Scheduling Window	-28 to -1		±2	±2	±2	±2	±2	±2	±2		±7	±7	±7	
Medical/ surgical history	X													
Prior anticancer medication/ procedures	X													
Prior/ Concomitant medication review	X	X	X	X	X	X	X	X	X	X	X		X	Concomitant medications will be recorded throughout the study and for 30 days after last dose. Off-study anticancer therapy will be recorded from study treatment discontinuation until time of death or until withdrawal from survival FU.
Cancer staging as appropriate for pediatric tumor type	X													

Study Period	Screening	Intervention Cycle = 28 Days					EOT	Post-treatment Visits			NOTES			
		1		2		3		4	5 – last	Safety FU		Efficacy (Imaging) FU Visits	Survival FU	
Visit Timing/ Cycle No.		1	8	15	1	15	1	1	1	At DC	30 days after last dose	Q8W for 24 weeks, then Q12W	Q12 W	
Cycle Day		1	8	15	1	15	1	1	1	At DC	30 days after last dose	Q8W for 24 weeks, then Q12W	Q12 W	
Scheduling Window	-28 to -1		±2	±2	±2	±2	±2	±2	±2		±7	±7	±7	
Tanner Staging	X	X								X		X	X	Tanner Stage will be assessed for all participants aged ≥8 years (females) or ≥9 years (males) during screening or C1D1, at EOT, and during efficacy and survival FU. During efficacy and survival FU, perform annually until puberty has completed or through survival FU, whichever comes first. Assessment can be performed by a local healthcare provider and reported by telephone contact if clinic visits are not possible for post-treatment visits after the 30-day safety FU.
Allocation		X												

Study Period	Screening	Intervention Cycle = 28 Days								EOT	Post-treatment Visits			NOTES
		1		2		3	4	5 – last	Safety FU		Efficacy (Imaging) FU Visits	Survival FU		
Visit Timing/ Cycle No.		1		2		3	4	5 – last	At DC	30 days after last dose	Q8W for 24 weeks, then Q12W	Q12 W		
Cycle Day		1	8	15	1	15	1	1	1					
Scheduling Window	-28 to -1		±2	±2	±2	±2	±2	±2	±2		±7	±7	±7	
Dental Evaluation	X	
Per local standard of care, but no less than annually.
 								X				
Dental examination by a dentist or qualified dental professional should be conducted per local institutional guidelines during screening (can occur up to 4 weeks after first dose). Dental examination after screening should occur per local standard of care, but no less than annually, and at EOT unless the most recent dental examination was done within the last 6 months, then the dental examination is not required.
 
Postbaseline dental examinations are not required for participants for whom permanent teeth (excluding third molars) are evaluated to be fully erupted at screening.

Study Period	Screening	Intervention Cycle = 28 Days					EOT	Post-treatment Visits			NOTES			
		1		2		3		4	5 – last	Safety FU		Efficacy (Imaging) FU Visits	Survival FU	
Visit Timing/ Cycle No.														
Cycle Day		1	8	15	1	15	1	1	1	At DC	30 days after last dose	Q8W for 24 weeks, then Q12W	Q12 W	
Scheduling Window	-28 to -1		±2	±2	±2	±2	±2	±2	±2		±7	±7	±7	
Telephone Contact or Visit			X											On C1D8, participants will have a telephone or clinic visit to assess for early toxicity and BP can be measured at home or at a local pharmacy for reporting at this visit. An unscheduled visit can occur prior to C1D15 if necessary for safety.

Study Period	Screening	Intervention Cycle = 28 Days					EOT	Post-treatment Visits			NOTES			
		1		2		3		4	5 – last	Safety FU		Efficacy (Imaging) FU Visits	Survival FU	
Visit Timing/ Cycle No.		1	8	15	1	15	1	1	1	At DC	30 days after last dose	Q8W for 24 weeks, then Q12W	Q12 W	
Cycle Day		1	8	15	1	15	1	1	1	At DC	30 days after last dose	Q8W for 24 weeks, then Q12W	Q12 W	
Scheduling Window	-28 to -1		±2	±2	±2	±2	±2	±2	±2		±7	±7	±7	
Vital Signs (BP, HR, RR, body temp, height, and weight)	X	X		X	X	X	X	X	X	X	X	X*	X*	Vital signs may be performed more frequently as clinically indicated. BP that is consistently above the 95th percentile for sex, age, and height/length requires further evaluation. Refer to hypertension guidelines in Section 6.6.2. BP monitoring will occur once every 2 weeks during the first 2 cycles, or more frequently if clinically indicated. Height and weight measurement will be obtained at C1D1 and thereafter at D1 of every cycle, and at EOT. *Height will also be monitored every 3 months in efficacy and survival follow-up until puberty has completed. Telephone contact is acceptable for height assessment if clinic visits are not possible at post-treatment visits after the 30-day safety FU.

Study Period	Screening	Intervention Cycle = 28 Days								EOT	Post-treatment Visits			NOTES
		1		2		3	4	5 – last	Safety FU		Efficacy (Imaging) FU Visits	Survival FU		
Visit Timing/ Cycle No.		1	8	15	1	15	1	1	1	At DC	30 days after last dose	Q8W for 24 weeks, then Q12W	Q12 W	
Scheduling Window	-28 to -1		±2	±2	±2	±2	±2	±2	±2		±7	±7	±7	
12-Lead ECG	X	X			X					X ^a	X	X		Single 12-lead ECG. If possible, participants must be in the recumbent position for a period of 5 minutes prior to the ECG. ECG should be conducted at Screening, C1D1, C2D1, and ^a D1 of every 4th cycle (ie, C6, C10, C14, etc.), EOT, and Safety FU. ECG at C1D1 and C2D1 should be conducted approximately 2 hours after lenvatinib dose. For high-risk participants (as defined in Section 8.3.4), conduct ECG monitoring in every cycle.
Echocardiogram or MUGA scan	X	Performed every 16 ± 2 Weeks after the first dose of study drug or sooner, if clinically indicated. 								X				
Lansky Play Score/ Karnofsky Performance Score	X	X			X		X	X	X	X	X			Scores obtained on C1D1 prior to allocation may also be used as the screening value to determine eligibility. Lansky Play Score will be used for participants up to and including 16 years of age. Karnofsky Performance Score will be used for participants >16 years of age.

Study Period	Screening	Intervention Cycle = 28 Days								EOT	Post-treatment Visits			NOTES
		1			2		3	4	5 – last		Safety FU	Efficacy (Imaging) FU Visits	Survival FU	
Visit Timing/ Cycle No.		1			2		3	4	5 – last	At DC	30 days after last dose	Q8W for 24 weeks, then Q12W	Q12 W	
Cycle Day		1	8	15	1	15	1	1	1					
Scheduling Window	-28 to -1		±2	±2	±2	±2	±2	±2	±2		±7	±7	±7	
Proximal Tibial growth plates x-ray	X									X ^a				For participants 2 to 17 years (≥18 years not required). X-ray of only 1 leg is required. ^a X-ray at EOT is required only for participants with open growth plates at screening and must be performed on the same leg as screening x-ray.
Laboratory Assessments														
Pregnancy Test	X	X			X		X	X	X	X	X			In WOCBP, a serum or urine pregnancy test (Appendix 2) will be performed at screening and at C1D1 prior to allocation (within 24 hours prior to the first dose of study drug), prior to D1 of every subsequent cycle, at EOT, and at the Safety FU visit. Results must be reviewed prior to administration of study drug on C1D1 and within 24 hours prior to dispensing study drug for all subsequent cycles.
Clinical Chemistry/ Hematology	X	X		X	X	X	X	X	X	X	X			Hematology and clinical chemistry can be performed within 7 days prior to the first dose of lenvatinib (C1D1) as part of the screening visit and do not

Study Period	Screening	Intervention Cycle = 28 Days					EOT	Post-treatment Visits			NOTES			
		1		2		3		4	5 – last	Safety FU		Efficacy (Imaging) FU Visits	Survival FU	
Cycle Day		1	8	15	1	15	1	1	1	At DC	30 days after last dose	Q8W for 24 weeks, then Q12W	Q12W	
Scheduling Window	-28 to -1		±2	±2	±2	±2	±2	±2	±2		±7	±7	±7	
														need to be repeated at C1D1, unless clinically indicated. Samples are to be obtained and assessed and the results reviewed prior to study drug administration on C1D1 and within 72 hours prior to the visit for all subsequent cycles. If ≥Grade 3 hematologic or clinical chemistry toxicity, repeat laboratory test and AEs assessment at least every 3 days (until improvement to <Grade 3). Results obtained on C1D1 prior to allocation may also be used as screening values to determine eligibility if assessed prior to allocation. Electrolytes such as potassium, calcium, and magnesium should be monitored and abnormalities, when considered clinically significant, should be corrected in all participants before starting treatment.

Study Period	Screening	Intervention Cycle = 28 Days								EOT	Post-treatment Visits			NOTES
		1			2		3	4	5 – last		Safety FU	Efficacy (Imaging) FU Visits	Survival FU	
Cycle Day		1	8	15	1	15	1	1	1	At DC	30 days after last dose	Q8W for 24 weeks, then Q12W	Q12W	
Scheduling Window	-28 to -1		±2	±2	±2	±2	±2	±2	±2		±7	±7	±7	
INR or PT	X													INR or PT should only be performed as part of the screening assessment and as clinically indicated.
Urine Dipstick (or urinalysis) Testing	X	X		X	X	X	X	X	X	X	X			Dipstick is the preferred method for urinalysis. Urine dipstick/urinalysis testing can be performed within 7 days prior to the first dose of lenvatinib (C1D1) as part of the screening visit and does not need to be repeated at C1D1 (unless clinically indicated) and within 72 hours prior to the visit at subsequent cycles. Urine dipstick/urinalysis testing will be performed during screening, at C1D1, C1D15, C2D1, C2D15, and D1 of every subsequent cycle, or more frequently as clinically indicated, at the EOT and at the Safety FU visit. For participants with proteinuria ≥2+ (≥100 mg/dL), urine dipstick/urinalysis testing should be performed on D15 (or more

Study Period	Screening	Intervention Cycle = 28 Days					EOT	Post-treatment Visits			NOTES			
		1		2		3		4	5 – last	Safety FU		Efficacy (Imaging) FU Visits	Survival FU	
Cycle Day		1	8	15	1	15	1	1	1	At DC	30 days after last dose	Q8W for 24 weeks, then Q12W	Q12W	
Scheduling Window	-28 to -1		±2	±2	±2	±2	±2	±2	±2		±7	±7	±7	
														frequently as clinically indicated) until the results have been 1+ or negative for 2 treatment cycles. If a new event of proteinuria ≥2+ (≥100 mg/dL) occurs, refer to Section 6.6.3 for further management guidelines. Urine glucose should be performed as part of the urine dipstick/urinalysis.
TSH, Free T4	X				X			X	X ^a	X	X			The screening blood sample for thyroid function testing can be obtained within 7 days prior to the first dose of lenvatinib (C1D1) as part of the screening visit and does not need to be repeated at C1D1 (unless clinically indicated) and within 72 hours prior to the visit at subsequent cycles. TSH and free T4 should be assessed for all participants. Assessment should be obtained at screening C2D1, ^a every 2 cycles thereafter, at EOT and at the Safety FU visit. If not done locally, can be done at a central laboratory.

Study Period	Screening	Intervention Cycle = 28 Days					EOT	Post-treatment Visits			NOTES		
		1		2		3		4	5 – last	Safety FU		Efficacy (Imaging) FU Visits	Survival FU
Visit Timing/ Cycle No.													
Cycle Day		1	8	15	1	15	1	1	1	At DC	30 days after last dose	Q8W for 24 weeks, then Q12W	Q12W
Scheduling Window	-28 to -1		±2	±2	±2	±2	±2	±2	±2		±7	±7	±7
Pharmacokinetics/Pharmacodynamics/Biomarkers													
PK blood samples, participants ≥13 kg body weight		X		X	X								PK blood samples drawn: 
 • C1D1: 0.5-4 hours and 6-10 hours postdose (no predose required) • C1D15: predose, 0.5-4 hours and 6-10 hours postdose • C2D1: predose and 2-12 hours postdose. Postdose samples are not needed if the lenvatinib administration is skipped. If dose interruption is necessary at these time points, contact the Sponsor. See Appendix 7 for country-specific requirement.

Study Period	Screening	Intervention Cycle = 28 Days								EOT	Post-treatment Visits			NOTES
		1			2		3	4	5 – last		Safety FU	Efficacy (Imaging) FU Visits	Survival FU	
Cycle Day		1	8	15	1	15	1	1	1	At DC	30 days after last dose	Q8W for 24 weeks, then Q12W	Q12W	
Scheduling Window	-28 to -1		±2	±2	±2	±2	±2	±2	±2		±7	±7	±7	
PK blood samples, participants <13 kg body weight		X		X	X									PK blood samples drawn: 
 • C1D1: 0.5-4 hours postdose (no predose required) • C1D15: 6-10 hours postdose (no predose required) • C2D1: predose and 2-12 hours postdose. Postdose samples are not needed if the lenvatinib administration is skipped. If dose interruption is necessary at these time points, contact the Sponsor. See Appendix 7 for country-specific requirement.
Buccal swab (DNA) for Genetic Analysis		X												Collection of buccal swabs to obtain genomic DNA will be performed at C1D1 prior to allocation. If sampling is not performed predose, sampling may occur at any subsequent visit.
Blood for serum biomarkers, participants ≥16 kg body weight		X		X	X		X		X	X				Collect predose: C1D1, C1D15, C2D1, C3D1, C5D1, and at EOT. See Appendix 7 for country-specific requirement.

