12. Male participants are eligible to participate if they agree to the following during the intervention period and for at least 7 days after the last dose of study intervention:
 - Be abstinent from heterosexual intercourse as their preferred and usual lifestyle (abstinent on a long term and persistent basis) and agree to remain abstinent

OR

- Must agree to use contraception unless confirmed to be azoospermic (vasectomized or secondary to medical cause [Appendix 5]) as detailed below:
 - Agree to use a male condom plus partner use of an additional contraceptive method when having penile-vaginal intercourse with a WOCBP who is not currently pregnant. Note: Men with a pregnant or breastfeeding partner must agree to remain abstinent from penile-vaginal intercourse or use a male condom during each episode of penile-vaginal penetration.
 - Contraceptive use by men should be consistent with local regulations regarding the methods of contraception for those participating in clinical studies. If the contraception requirements in the local label for any of the study interventions is more stringent than the requirements above, the local label requirements are to be followed.

Female Participants

13. A female participant is eligible to participate if she is not pregnant or breastfeeding, and at least one of the following conditions applies:

- Is not a WOCBP

OR

- Is a WOCBP and using a contraceptive method that is highly effective (with a failure rate of <1% per year), with low user dependency, or be abstinent from heterosexual intercourse as their preferred and usual lifestyle (abstinent on a long term and persistent basis), as described in Appendix 5 during the intervention period and for at least 30 days post lenvatinib.
- A WOCBP must have a negative highly sensitive pregnancy test ([urine or serum] as required by local regulations) within 24 hours before the first dose of study intervention.
- If a urine test cannot be confirmed as negative (eg, an ambiguous result), a serum pregnancy test is required. In such cases, the participant must be excluded from participation if the serum pregnancy result is positive.
- Additional requirements for pregnancy testing during and after study intervention are located in Appendix 2.
- The investigator is responsible for review of medical history, menstrual history, and recent sexual activity to decrease the risk for inclusion of a woman with an early undetected pregnancy.

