8.4 Adverse Events, Serious Adverse Events, and Other Reportable Safety Events

The definitions of an AE or SAE, as well as the method of recording, evaluating, and assessing causality of AE and SAE and the procedures for completing and transmitting AE, SAE, and other reportable safety event reports can be found in Appendix 3.

Adverse events, SAEs, and other reportable safety events will be reported by the participant (or, when appropriate, by a caregiver, surrogate, or the participant's legally authorized representative).

The investigator and any designees are responsible for detecting, documenting, and reporting events that meet the definition of an AE or SAE as well as other reportable safety events. Investigators need to document if an SAE was associated with a medication error, misuse, or abuse. Investigators remain responsible for following up AEs, SAEs, and other reportable safety events for outcome according to Section 8.4.3.

The investigator, who is a qualified physician, will assess events that meet the definition of an AE or SAE as well as other reportable safety events with respect to seriousness, intensity/toxicity and causality.

Progression of the cancer under study is not considered an AE as described in Section 8.4.6 and Appendix 3.

8.4.1 Time Period and Frequency for Collecting AE, SAE, and Other Reportable Safety Event Information

All AEs, SAEs, and other reportable safety events that occur after the participant provides documented informed consent but before intervention allocation must be reported by the investigator if the participant is receiving placebo run-in or other run-in treatment, if the event cause the participant to be excluded from the study, or is the result of a protocol-specified intervention, including but not limited to washout or discontinuation of usual therapy, diet, or a procedure.

- All AEs from the time of intervention allocation through 30 days following cessation of study intervention must be reported by the investigator.
- All AEs meeting serious criteria, from the time of intervention allocation through 30 days following cessation of study intervention.
- All pregnancies and exposure during breastfeeding, from the time of intervention allocation through 30 days following cessation of study intervention.

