8.11.5 Post-treatment Visits

8.11.5.1 Safety Follow-up Visit

The mandatory Safety Follow-up Visit should be conducted approximately 30 days after the last dose of study intervention or before the initiation of a new anticancer treatment, whichever comes first.

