9.6.2 Statistical Methods for Safety Analyses

Safety and tolerability will be assessed by clinical review of all relevant parameters, including AEs, laboratory tests, and vital signs. Safety summaries will be pooled across all indications. The additional safety analyses for each tumor type might be conducted if desired and will be documented in the sSAP. The safety analysis population will be used for the analysis of safety data. TEAE is defined as all AEs from the treatment start date until 30 days after last dose (30 days for SAE). The incidence of TEAEs and SAEs will be summarized by system organ class and preferred term. Continuous measures such as changes from baseline in laboratory test data, vital signs, 12-lead ECGs, cardiac function by echocardiography or MUGA scan, urine dipstick, and Lansky play scores or KPS scores will be summarized using descriptive statistics (mean, standard deviation, etc.) for baseline, on-treatment, and change-from-baseline values.

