10.2 Appendix 2: Clinical Laboratory Tests

- The tests detailed in [Table 7](#) will be performed by the local laboratory.
- Protocol-specific requirements for inclusion or exclusion of participants are detailed in Sections 5.1 and 5.2 of the protocol.
- Additional tests may be performed at any time during the study as determined necessary by the investigator or required by local regulations.
- Pregnancy testing:
 - Pregnancy testing requirements for study inclusion are described in Section 5.1.
 - Pregnancy testing (urine or serum as required by local regulations) should be conducted at monthly intervals during intervention.
 - Pregnancy testing (urine or serum as required by local regulations) should be conducted at the end of relevant systemic exposure and correspond with the time frame for female participant contraception in Section 5.1.
 - Additional serum or urine pregnancy tests may be performed, as determined necessary by the investigator or required by local regulation, to establish the absence of pregnancy at any time during the subject's participation in the study.

Table 7 Protocol-required Safety Laboratory Assessments

Laboratory Assessments	Parameters			
Hematology	Platelet Count Red Blood Cell (RBC) Count Hemoglobin Hematocrit International Normalized Ratio (INR) or prothrombin time (PT) ^a	White Blood Cell (WBC) count with Differential: Neutrophils Lymphocytes Monocytes Eosinophils Basophils		
Chemistry	Renal Function Tests	Electrolytes^c	Liver Function Tests	Other Chemistries
	Blood urea nitrogen (BUN) ^b Creatinine	Potassium Carbon dioxide (CO ₂) or bicarbonate ^d Sodium Calcium Chloride Magnesium Phosphorous	Aspartate aminotransferase (AST) Alanine aminotransferase (ALT) Alkaline phosphatase Total bilirubin Direct bilirubin ^e	Albumin Amylase Lipase Glucose ^f Lactate dehydrogenase Total protein
Thyroid Function Tests	Thyroid-stimulating hormone (TSH) Free thyroxine (T4)			
Urine dipstick/urinalysis testing, ^{f, g}	
 Glucose, protein, blood Urinalysis for microscopy^g: Microscopic examination for RBCs/high-power field. 			
Other Screening Tests	
 Serum or urine β human chorionic gonadotropin (β-hCG) pregnancy test (as needed for women of child-bearing potential [WOCBP]). 			

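### The Safety Follow-up visit may fall on Day 23 or earlier while AE reporting and the TEAE window run to Day 30, so late events may be under-ascertained; the last pregnancy test in Table 1 can also precede the time frame in Appendix 2

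*Combined protocol and SAP*

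**What the plan says.** Days below are counted from the last dose of lenvatinib.

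- **Visit timing.** The Safety Follow-up column of Table 1 reads "30 days after last dose" and carries a scheduling window of ±7 days. Section 8.11.5.1 makes the visit mandatory at approximately 30 days "or before the initiation of a new anticancer treatment, whichever comes first".
- **Reporting period.** Section 8.4.1 states: "All AEs from the time of intervention allocation through 30 days following cessation of study intervention must be reported by the investigator". It sets the same limit for serious events, "All AEs meeting serious criteria, from the time of intervention allocation through 30 days following cessation of study intervention", and for pregnancies, "All pregnancies and exposure during breastfeeding, from the time of intervention allocation through 30 days following cessation of study intervention". The synopsis likewise promises 30 days of follow-up for AEs and SAEs.
- **Analysis window.** Section 9.6.2: "TEAE is defined as all AEs from the treatment start date until 30 days after last dose (30 days for SAE").
- **Pregnancy testing.** In Table 1 and Section 8.3.6.6 the last scheduled test is at the Safety Follow-up visit; the efficacy and survival follow-up columns show none. Appendix 2 says that testing "should be conducted at the end of relevant systemic exposure and correspond with the time frame for female participant contraception in Section 5.1". For women of childbearing potential, criterion 13 in Section 5.1 sets that time frame as "during the intervention period and for at least 30 days post lenvatinib".
- **Next contact.** Under Section 8.11.5.3, participants who do not enter efficacy follow-up have their first survival assessment 12 weeks after the later of the discontinuation and safety visits.

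**The concern.** The visit window is symmetric around Day 30, but the periods that the visit serves end at Day 30. A visit on the early side of the window is on schedule and still stops short of the end of the reporting and TEAE periods. Section 8.4.2 names open-ended verbal questioning as the preferred way to detect AEs, and that needs a contact. After an early visit the remaining days appear to depend on the participant or family volunteering information.

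Safety is a secondary objective, and TEAE incidence is summarised over a fixed window for everyone in the Safety Analysis Set. If active questioning ends at different times for different participants, the tables will not show who was asked about the whole window. The pregnancy-test passages raise a separate matter of consistency: a site that follows Table 1 exactly may not meet Appendix 2.

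**Working it through.** The check is date arithmetic plus a comparison of passages. No sample size, power or alpha figure is involved.

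**1. The visit range in Table 1.** Nominal Day 30, window ±7.
- Earliest: 30 − 7 = Day 23.
- Latest: 30 + 7 = Day 37.

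**2. Days of the 30-day window left after a visit on Day v.** Formula: max(0, 30 − v).

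| Visit day | Days left | Share of 30 days |
|---|---|---|
| 23 (earliest in window) | 7 | 7/30 = 23.3% |
| 26 | 4 | 4/30 = 13.3% |
| 30 to 37 | 0 | 0% |
| 14 (assumed, brought forward) | 16 | 16/30 = 53.3% |
| 10 (assumed, brought forward) | 20 | 20/30 = 66.7% |

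The last two rows are examples of the Section 8.11.5.1 provision. The documents do not say how often or how early visits are brought forward.

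**3. Average over in-window visits.** The documents give no distribution of visit days. The possible range is 0 days lost (every visit on Day 30 or later) to 7 days lost (every visit on Day 23). As an illustration only, suppose that visits are spread evenly over the 15 days from Day 23 to Day 37:
- Early visits: 7/15 = 46.7%.
- Total days lost: 7 + 6 + 5 + 4 + 3 + 2 + 1 = 28.
- Mean among early visits: 28/7 = 4 days (13.3% of the window).
- Mean over all visits: 28/15 = 1.9 days (1.87/30 = 6.2% of the window).

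**4. When the next scheduled contact falls.** For a participant who goes directly to survival follow-up after a Day 23 visit: 23 + 12 × 7 = 23 + 84 = Day 107, ±7 days. That is well after Day 30. For a participant in efficacy follow-up, an imaging visit could fall in Days 24 to 30, but only by coincidence.

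**5. The pregnancy test.** Table 1 permits the last scheduled test on Day 23. Section 5.1 sets a contraception period of at least 30 days for women of childbearing potential, and Appendix 2 links the end-of-exposure test to that period. A Day 23 test is up to 7 days short of it, and more if the visit is brought forward.

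**The case against.** The strongest reply is that the plan's duties are set by date, not by visit. The investigator must report events through Day 30 whenever the visit took place, concomitant medication is recorded for 30 days after the last dose, and TEAEs are classified by event date. All of this stands, and it rules out several stronger readings.

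- **A reader might infer that events on Days 24 to 30 drop out of the analysis, or that TEAEs are undercounted.** The documents do not support this. Such events must still be reported and still count as TEAEs whenever they come to light. An undercount is possible, not shown, and nothing in the documents supports a claim that it would vary by site. With one arm and descriptive summaries, no between-arm comparison can be biased.
- **A reader might infer that the plan schedules no AE inquiry at all after an early visit.** The text available here cannot establish that. Table 1 as supplied stops at the serum biomarker row. Its AE row, with any note on a Day 30 contact, is not in that text, and neither are the imaging, physical examination and palatability rows. What can be said is that no readable passage schedules such an inquiry.
- **A reader might infer that no pregnancy test is called for at the end of the period.** Appendix 2 does call for one. The defect is that Table 1 and Appendix 2 do not agree. The synopsis also describes post-treatment pregnancy capture as by spontaneous report, so reporting does not hang on a test.
- **A reader might apply the 30-day contraception period to everyone.** It covers women of childbearing potential; the minimum for male participants in Section 5.1 is 7 days.

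It can also be said that ±7 is simply the window used for all three types of post-treatment visit. That explains the choice, but for imaging and survival visits no reporting or analysis period ends on the nominal day. For the safety visit one does.

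**Conclusion.** The point holds as a minor one. A visit that follows Table 1 exactly can end scheduled safety ascertainment up to 7 days (23%) before the TEAE window closes, and Section 8.11.5.1 allows a longer gap. The gap is zero for any visit on Day 30 to Day 37. Late TEAEs may be under-ascertained; how many cannot be estimated from the documents. The average of about 1.9 days per participant rests wholly on an assumed even spread of visits and excludes visits brought forward.

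Separately, the pregnancy-test timing in Table 1 is inconsistent with Appendix 2 read together with Section 5.1, for women of childbearing potential.

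The conclusion on AE inquiry is conditional on the AE row of Table 1: if that row already requires a contact on or after Day 30, this part is answered. The primary analysis of objective response at Week 16 is not affected.

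**What to change.** 1. In Table 1, make the Safety Follow-up window one-sided: Day 30 to Day 37 (0/+7). Every in-window visit then covers the full AE, SAE, pregnancy-reporting and TEAE period, since max(0, 30 − v) = 0 for v from 30 to 37.
2. In Section 8.11.5.1, add a sentence: where the visit is brought forward because of new anticancer treatment, a telephone contact on or after Day 30 asks about AEs and SAEs.
3. Reconcile the pregnancy-test timing in Table 1 (and Section 8.3.6.6) with Appendix 2 and Section 5.1, including for visits brought forward. A telephone AE contact does not settle that question.

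The cost is one changed window, one added sentence and an alignment of the testing passages. Sites lose some scheduling flexibility, and participants whose visit is brought forward have one extra telephone contact. How many that would be is not stated in the documents.
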